**7.4.1. Number and proportion of subjects who successfully withdrawal from all IS after darTregs infusion**

**Variable:** Complete withdrawal from all IS

**Analysis:** Proportion with exact binomial 95% confidence limits

**7.4.2. Duration that subjects tolerate complete IS discontinuation**

**Variable:** Time off all IS

**Analysis:** Kaplan-Meier estimates of time to re-initiation of IS after completion of ISW (or censoring if no re-initiation occurs by the end of study). Duration will be displayed graphically with a Kaplan-Meier curve and the corresponding median and two-sided 95% confidence interval.

**7.4.3. Number and proportion of subjects who successfully withdrawal from all IS after darTregs infusion and are operationally tolerant**

**Variable:** Complete withdrawal from all IS and meets definition of operational tolerance (Protocol section 5.4)

**Analysis:** Proportion with exact binomial 95% confidence limits

**7.5. Secondary Safety Endpoints**

All secondary safety endpoint analyses will use the ITT1 population, with a sensitivity analysis using the PP population unless otherwise stated.

**7.5.1. Rate of composite outcome measure including refractory AR, CR, re-transplantation, and death**

**Variable:** Occurrence of refractory AR, CR, re-transplantation, or death

**Analysis:** Proportion with exact binomial 95% confidence limits

**7.5.2. Incidence of biopsy proven or clinical AR and/or CR**

**Variable:** Biopsy proven or clinical AR or CR

**Analysis:** Proportion with exact binomial 95% confidence limits; Also number of biopsy proven or clinical AR and/or CRAEs

**7.5.3. Timing of biopsy proven or clinical AR and/or CR in ITT2 population**

**Variable:** Time to biopsy proven or clinical AR and/or CR

**Analysis:** Kaplan-Meier estimates of time to re-initiation of IS after completion of ISW (or censoring if no rejection occurs by the end of study). Duration will be displayed

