Secondary Safety Endpoint	The trial will assess the safety of IS withdrawal in the context of darTregs therapy by describing the following secondary safety endpoints: 
 
1. Rate of composite outcome measure including refractory acute rejection, chronic rejection, re- transplantation, and death
 
2. Incidence of biopsy proven or clinical acute rejection and/or chronic rejection
 
3. Timing of biopsy proven or clinical acute rejection and/or chronic rejection
 
4. Severity of biopsy proven acute rejection and/or chronic rejection
 

Primary Efficacy Endpoint	The efficacy of a single IV dose of darTregs will be assessed by the number and proportion of LT subjects who are able to reduce CNI dosing by 75% and discontinue a 2 nd IS drug (if applicable) with stable liver tests for at least 12 weeks. The frequency of successful CNI minimization will be compared to historical cohorts of comparable adult LT recipients undergoing IS withdrawal.
Secondary Efficacy Endpoints	The efficacy of a single IV dose of darTregs infusion will be assessed by determining the number and percentage of subjects who have received darTregs and are identified as operationally tolerant, defined by maintaining stable allograft function (assessed by liver tests) and histology (determined by central pathologist reading in comparison to screening liver biopsy at study entry) in the absence of IS for one year. The frequency of tolerance will be compared to historical cohorts of adult liver transplant recipients undergoing IS withdrawal.
Primary Mechanistic Endpoints	The level and persistence of deuterium-labeled darTregs in the circulation will be determined by serial measurements of deuterium content in DNA from purified peripheral blood Tregs after darTregs infusion using gas chromatography-mass spectrometry (GC-MS) testing.
Secondary Mechanistic Endpoints	The overall increase of darTregs in circulation will be assessed using the alloreactive T cell frequency (ATF) assay

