Treatment Description	All eligible participants will initiate IS withdrawal. Approximately 10-12 weeks after initiating IS withdrawal, subjects will have autologous Tregs collected for darTregs manufacturing. 
During the last 2 weeks of IS withdrawal Step 2 (CNI reduced by 25%), a single total dose of 400 x 10^6 ± 100 deuterium-labeled darTregs will be infused intravenously. The subject will then, if eligible, resume IS withdrawal within 2 weeks after darTregs infusion (see Section entitled "Resumption of IS Withdrawal after darTregs Infusion" below). Only subjects who receive 300-500 x 10^6 darTregs and who meet the primary endpoint of 75% reduction in CNI from baseline after darTregs will be offered the opportunity to continue IS withdrawal until complete discontinuation of IS (secondary endpoint). Those who receive 100-300 x 10^6 darTregs will only be allowed to proceed to the primary endpoint but will not be eligible for complete IS withdrawal.

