#### 4. ANALYSIS SAMPLES

The summary descriptive analyses will be performed on the following subject populations:

1. All subjects who give informed consent and undergo the screening liver biopsy (Safety Sample).
2. The Intent-to-treat I sample (ITT1) will be defined as all subjects who initiate IS withdrawal
3. The Intent-to-treat II sample (ITT2) will be defined as all subjects who receive darTregs.
4. The Per-Protocol sample (PP) will be defined as all subjects who receive at least 300 x 10^6 cells of darTregs.

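### SAP 7.5.3 analyses time to rejection with the wrong event and a clock that starts only at complete withdrawal, so rejections between infusion and complete withdrawal never enter the curve

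*SAP*

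**What the plan says.** The synopsis introduces the secondary safety endpoints with "The trial will assess the safety of IS withdrawal in the context of darTregs therapy". The third of the four is "Timing of biopsy proven or clinical acute rejection and/or chronic rejection", with no restriction to the period after immunosuppression has stopped.

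SAP Section 7.5.3 assigns this endpoint to ITT2 and gives the variable as "Time to biopsy proven or clinical AR and/or CR". The analysis line then reads "Kaplan-Meier estimates of time to re-initiation of IS after completion of ISW (or censoring if no rejection occurs by the end of study".

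Section 7.4.2, the secondary efficacy endpoint on time off all immunosuppression, reads "Kaplan-Meier estimates of time to re-initiation of IS after completion of ISW (or censoring if no re-initiation occurs by the end of study".

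On the population, Section 4 states "The Intent-to-treat II sample (ITT2) will be defined as all subjects who receive darTregs". The Treatment Description in the synopsis says that subjects given 100-300 x 10^6 cells "will only be allowed to proceed to the primary endpoint but will not be eligible for complete IS withdrawal".

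**The concern.** The Section 7.5.3 analysis does not estimate the variable named directly above it. It appears to have been carried over from Section 7.4.2 with one word changed. There are three consequences.

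- **Event.** Restarting immunosuppression is not rejection. A subject who restarts without rejecting is an event under the first half of the sentence and censored under the second.
- **Origin.** The clock starts when withdrawal is complete. An infused subject who rejects before that point has no time zero when the rejection occurs.
- **Population.** The lower-dose subjects belong to ITT2 but cannot reach the time origin, so they are excluded by construction.

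The endpoint is there to describe when rejection occurs as immunosuppression is reduced. The curve as specified describes only subjects who have already come through the whole taper. A reader could take it as reassuring about the period it leaves out.

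**Working it through.** The SAP states no figure for this endpoint, so there is none to reproduce. The check is a comparison of the text, followed by an illustration of size.

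**Comparison of the two analyses**

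| Element | 7.4.2 (time off all IS) | 7.5.3 (time to rejection) | Needed for the 7.5.3 variable |
|---|---|---|---|
| Event | re-initiation of IS | re-initiation of IS | first AR or CR |
| Origin | completion of withdrawal | completion of withdrawal | a date every ITT2 subject has |
| Censored if | no re-initiation | no rejection | no rejection |
| Population | ITT2 | ITT2 | ITT2 |

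Only the censoring condition was adapted. No other section supplies a different event or origin.

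**Who has a time zero.** Infusion takes place in withdrawal Step 2, with CNI reduced by 25% (synopsis, Treatment Description). Complete withdrawal is then offered only to subjects who received 300-500 x 10^6 cells and met the primary endpoint of 75% CNI reduction. Section 7.2.1 requires stable liver tests for at least 12 weeks to meet that endpoint. The risk set is therefore selected on having passed most of the taper without trouble.

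**Share of ITT2 outside the risk set.** Input: up to 11 subjects for infusion (synopsis, Accrual Objective). The numbers of completers are assumed. Share = (N - completers)/N.

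- 2 completers: (11 - 2)/11 = 9/11 = 82%
- 4 completers: (11 - 4)/11 = 7/11 = 64%
- 6 completers: (11 - 6)/11 = 5/11 = 45%

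The Study Duration row of the synopsis gives nine rather than 11. With N = 9 the shares are 7/9 = 78%, 5/9 = 56% and 3/9 = 33%.

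**Share of rejections lost.** Let t be rejections after infusion but before completion, p rejections after completion, and l non-rejecting subjects not eligible for complete withdrawal. Assume everyone else completes. Then completers c = 11 - t - l. Even on the generous reading that the event is rejection, the written origin gives p events among c subjects. The infusion origin gives t + p among 11. The share lost is t/(t + p).

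| t | l | p | Written origin, p/c | Infusion origin | Lost |
|---|---|---|---|---|---|
| 2 | 0 | 2 | 2/9 | 4/11 | 2/4 = 50% |
| 4 | 0 | 1 | 1/7 | 5/11 | 4/5 = 80% |
| 4 | 2 | 1 | 1/5 | 5/11 | 4/5 = 80% |
| 6 | 2 | 0 | 0/3 | 6/11 | 6/6 = 100% |
| 8 | 2 | 1 | 1/1 | 9/11 | 8/9 = 89% |

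Over the assumed grid (t from 2 to 8, p from 0 to 2, l of 0 or 2), the loss runs from 50% to 100%.

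**Which rejections the error costs.** Acute rejection after the start of withdrawal excludes a subject from infusion (synopsis, darTregs Infusion Exclusion Criteria), so such a subject is not in ITT2 under any origin. The error removes the rejections between infusion and completion of withdrawal.

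**The case against.** The strongest reply is that the intent is recoverable. The heading, the variable and the censoring clause all point to rejection, so a programmer would see the contradiction and raise a query rather than silently produce the wrong curve. For the same reason the output would not necessarily be a copy of the Section 7.4.2 curve, because the censoring clauses differ. This is fair as regards the event. It does not settle the origin: neither the heading nor the variable gives one, and the only origin written is unusable for much of ITT2. The choice would then be made after rejection dates are known in an open-label trial.

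Second, the reach is limited. This is one of four secondary safety endpoints, descriptive, single-arm and without a test. Incidence is still reported in ITT1 (Section 7.5.2), severity in Section 7.5.4, and rejection among the adverse events of interest (Section 8.2). That stands, but none of these gives timing.

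Third, the percentages rest on assumed counts. That also stands. They show scale and are not predictions.

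Fourth, infusion is not the only defensible origin. A clock from the start of withdrawal with delayed entry at infusion would also be valid. That is correct, although infusion is simpler.

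**Conclusion.** The concern holds. As written, Section 7.5.3 does not estimate time to rejection in ITT2. Its event contradicts its own variable and censoring rule, and its origin exists only for subjects who complete withdrawal. Every rejection between infusion and complete withdrawal falls before time zero and is left out, and the 100-300 x 10^6 group is excluded entirely.

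In the illustrations, 45% to 82% of 11 infused subjects (33% to 78% of nine) have no place in the curve, and 50% to 100% of post-infusion rejections are lost. These figures depend on assumed numbers of completers and rejections, but the structural exclusion does not. The damage is confined to the timing analysis. It should be corrected before analysis because the stated rule gives a wrong result, not merely an imprecise one.

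**What to change.** Replace the analysis sentence in Section 7.5.3 with: Kaplan-Meier estimate of the time from darTregs infusion to the first biopsy-proven or clinical AR or CR in ITT2, with subjects free of rejection censored at last follow-up. Keep the existing plot, median and two-sided 95% confidence interval.

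A plain ITT2 curve should not start at the beginning of withdrawal. Acute rejection before infusion keeps a subject out of ITT2, so the 12 to 14 weeks before infusion (synopsis, Study Design) would be guaranteed free of acute rejection. If that time scale is preferred, use delayed entry at infusion.

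Optionally, add an ITT1 curve from the start of withdrawal. It would show the timing of pre-infusion rejections and match the population of Section 7.5.2.

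The cost is one sentence of SAP text. The stated variable already requires rejection dates, and every ITT2 subject has an infusion date, so no new data are needed.

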**graphically with a Kaplan-Meier curve and the corresponding median and two-sided 95% confidence interval.**

**7.5.4. Severity of biopsy proven or clinical AR and/or CR in ITT2 population**

**Variable:** Biopsy proven or clinical AR or CR

**Analysis:** Proportion of subjects in each observed BANFF severity category

## 8. SAFETY EVALUATION

### 8.1. Overview of Safety Analysis Methods

All safety analyses will be carried out using the safety sample defined in Section 4 unless otherwise noted. Missing safety information will not be imputed. These analyses will not be stratified by site.

### 8.2. Adverse Events

All AEs will be classified by system organ class (SOC) and preferred term, according to a standardized thesaurus (Medical Dictionary for Regulatory Activities [MedDRA] version 18.0). The severity of AEs will be classified using the National Cancer Institute's (NCI's) Common Toxicity Criteria for Adverse Events (CTCAE) version 4.0. Each AE is entered on the electronic case report form (eCRF) once at the highest severity. As such, no additional data manipulation is needed to identify events.

An overall summary table will be developed to report the number of events and the number and percentage of subjects having at least one event in the following categories:

- AEs
- AEs indicated as serious
- AEs of interest (Acute Rejection, Clinical Rejection, Chronic Rejection, Malignancy, Study defined Grade 3 or higher infections, and Grade 3 or higher Infusion Reactions) AEs that lead to study drug discontinuation
- AEs with an outcome of death
- SAEs that were reported as being related to ISW or darTregs
- AEs reported by severity

In addition, AEs classified by MedDRA SOC and preferred term will be summarized for each treatment group and overall for each of the following:

- All AEs
- AEs by maximum severity
- AEs by relationship to ISW or darTregs (site investigator determination)

Summary tables will present the total number of events as well as the number and percentage of subjects experiencing the events. If a subject experiences the same AE on multiple occasions, the event will be counted once for each occurrence when reporting the number of AEs. When reporting the number of subjects experiencing the events, a subject will only be

counted once if they experience an event within the particular SOC or preferred term. Percentages will be based on the number of subjects in the safety population.

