## 1. PROTOCOL SYNOPSIS

Title	Safety of Donor Alloantigen Reactive Tregs (darTregs) to Facilitate Minimization and/or Discontinuation of Immunosuppression in Adult Liver Transplant Recipients ( ARTEMIS )
Short Title	darTregs for CNI Reduction
Protocol Number	CTOTC-12
ClinicalTrials.gov Identifier	NCT02474199
Clinical Phase	Phase I/II
Primary Safety Objective	This study will evaluate the safety and tolerability of a single IV dose of the darTregs product.
Secondary Safety Objective	This study will evaluate the safety of immunosuppression (IS) 1) minimization and 2) discontinuation after one IV dose of darTregs.
Primary Efficacy Objective	The study will evaluate the ability of a single IV dose of darTregs to reduce baseline, standard of care (SOC) calcineurin inhibitor (CNI) dosing by 75% along with discontinuation of either prednisone or mycophenolate mofetil (MMF), as applicable.
Secondary Efficacy Objective	This study will determine whether a single IV dose of darTregs can induce operational tolerance.
Mechanistic Objectives	We will assess the pharmacokinetic profile of darTregs by measuring the level of deuterium-labeled Tregs in circulation. Potential impact of darTregs therapy on immunological profiles will be assessed by comparing leukocyte phenotypes, tissue histology and gene expression in protocol and for-cause biopsies, and alloantibody before and after darTregs infusion.
Study Design	A multi-center, open-label clinical trial in adult liver transplant recipients with two primary interventions: 
 
• administration of a single IV dose of darTregs and
 
• reduction of IS dosing with possible complete IS discontinuation.
 
 Adult living donor liver recipients two to six years after LT will initiate IS withdrawal. Twelve to 14 weeks later, they will receive a single dose of darTregs and continue IS withdrawal.
Primary Safety Endpoint	The safety and tolerability of a single infusion of darTregs administered to LT recipients will be assessed 24 weeks after darTregs by describing: 
 
1. Occurrence of CTCAE Grade 3 or higher adverse events (AEs) attributable to the darTregs infusion including infusion reaction / cytokine release syndrome
 
2. Occurrence of study defined Grade 3 or higher infections
 
3. Occurrence of any malignancy, including PTLD
 

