### **8.4. Clinical Laboratory Evaluation**

Clinical laboratory measurements include serum chemistry, urinalysis, and hematology. Results will be converted to standardized units where possible. For numeric laboratory results, descriptive statistics of laboratory values and the change from baseline of laboratory values will be presented for each analysis sample and overall. For categorical laboratory results, the number and percentage of subjects reporting each result will be presented for each analysis sample and overall.

Liver test data will be plotted to show patterns over time. For each test with a numeric result, data will be plotted as a spaghetti plot where each subject's values will be plotted and connected by line segments, forming one line per subject. For each test with a numeric result, quantile plots with treatment group means (or medians) as well as 25th and 75th percentiles plotted over time will be created. Tests with qualitative results (such as "present" or "positive") will not be plotted. Normal ranges will also be plotted using Harrison's normal range.

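### The general AE and SAE tables are split by an undefined treatment group, not by period relative to infusion, and their denominator includes subjects never infused

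*SAP*

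**What the plan says.** The Study Design row of the synopsis (SAP Section 1) describes "A multi-center, open-label clinical trial in adult liver transplant recipients with two primary interventions": the darTregs infusion and the reduction of immunosuppression (IS). All subjects start withdrawal first, and "Twelve to 14 weeks later, they will receive a single dose of darTregs and continue IS withdrawal".

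Section 4 defines four samples: Safety (consented and had the screening biopsy), ITT1 (started withdrawal), ITT2 (received darTregs) and PP (received at least 300 x 10^6 cells). None is called a treatment group.

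On adverse events, Section 8.2 says: "In addition, AEs classified by MedDRA SOC and preferred term will be summarized for each treatment group and overall". The tables listed are all AEs, AEs by maximum severity, and AEs by relationship to withdrawal or darTregs as judged by the site investigator. Section 8.1 sets the analysis set: "All safety analyses will be carried out using the safety sample defined in Section 4 unless otherwise noted". Section 8.2 sets the denominator: "Percentages will be based on the number of subjects in the safety population". Section 8.3 summarises SAEs in the same manner (its cross-reference is garbled and is read here as pointing to 8.2). Section 8.2 also says that each AE is entered once, at its highest severity.

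Section 8.4 uses the same label for liver tests: "quantile plots with treatment group means (or medians) as well as" quartiles over time.

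**The concern.** A programmer cannot build a by-group table when no group is defined. The larger problem lies behind the label. Section 8 gives no rule that sorts an AE into before or after infusion, and the denominator is not restricted to infused subjects.

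The primary safety objective is the safety and tolerability of one darTregs dose. In the tables as specified, an event that darTregs cannot have caused, because it came before infusion or in a subject never infused, sits in the same cell as one that they may have caused. The design offers a descriptive comparison of the same subjects before and after infusion, and these tables do not use it.

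The SAP itself treats the distinction as important elsewhere. The stopping rules in Section 1 separate events at any time in the study from events after infusion. Acute rejection after the start of withdrawal bars a subject from infusion, yet the AEs-of-interest row in 8.2 counts that rejection together with rejection after infusion.

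**Working it through.** The SAP gives no figure on this point to reproduce. The check is a reading of the text followed by an illustration of the denominator effect.

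**Reading**

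1. Groups: Section 1 describes one cohort with two interventions in sequence, and Section 4 defines only nested samples. The term used in 8.2 and 8.4 has no definition.
2. Periods: Section 8 has no onset-period split and no treatment-emergent rule. Deleting the stray label would not separate pre-infusion from post-infusion events.
3. Denominator: by 8.1 and 8.2 it is the safety sample, which includes subjects who never start withdrawal or are never infused.

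Points 2 and 3 produce the pooling. Point 1 leaves the table layout undefined.

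**Illustration of dilution**

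Inputs, from the Accrual Objective in Section 1: up to 18 enrolled, taken as the safety sample, and up to 11 eligible for both withdrawal and infusion, taken as ITT2. The Study Duration row speaks of nine such patients, so 9 is shown as well. The actual numbers are unknown.

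For x infused subjects with a post-infusion event, the percentage is x/n. Exact (Clopper-Pearson) limits are Beta⁻¹(0.025; x, n−x+1) and Beta⁻¹(0.975; x+1, n−x). For x = 0 the upper limit is 1 − 0.025^(1/n). Section 8.2 plans counts and percentages only, so the intervals are added here to show precision.

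| Denominator | x = 2 | 95% CI | x = 0, upper limit |
|---|---|---|---|
| 18 (as specified) | 11.1% | 1.4 to 34.7 | 18.5% |
| 11 (infused) | 18.2% | 2.3 to 51.8 | 28.5% |
| 9 (infused) | 22.2% | 2.8 to 60.0 | 33.6% |

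The percentage shown is the infused-subject percentage times 11/18 = 0.61, or 9/18 = 0.50 if nine are infused. If every subject in the safety sample were infused, the factor would be 1. The dilution would then vanish, but the mixing of pre- and post-infusion events would remain.

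**The case against.** The strongest reply is that the plan already reports safety after infusion elsewhere. Section 7.3 assesses attributable Grade 3 or higher AEs, study-defined Grade 3 or higher infections, and malignancy at 24 weeks after darTregs, both combined and individually. The infection and malignancy components do not depend on attribution. Section 8.2 tabulates AEs by relationship and lists Grade 3 or higher infusion reactions. Sections 7.5.3 and 7.5.4 analyse rejection in ITT2. With at most 18 enrolled, listings are also workable.

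Much of this stands. A reader might infer that the plan cannot show what followed the infusion, and the documents do not support that. The gap is narrower: lower-grade events, events not attributed to darTregs other than infections and malignancy, and events after 24 weeks fall to the general tables (rejection apart). Attribution is also not timing. It is made open-label while withdrawal continues, and the overall summary puts SAEs related to either intervention on one line. The primary analysis in 7.3.2 uses ITT1, which can itself include subjects never infused.

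It can also be said that treatment group might mean infused against never infused, or the two cell-count categories in Section 6.2. That is fair. The supportable statement is that the term is undefined, not that it must collapse to a single column.

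For liver tests the objection largely succeeds. Section 8.4 plots one line per subject over time and summarises laboratory values by analysis sample, so only the label on the quantile plots is wrong.

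**Conclusion.** The point holds for the general AE tables in 8.2 and the SAE tables in 8.3. As written they combine pre-infusion, post-infusion and never-infused experience, and they understate post-infusion percentages by a factor of about 0.61 at the stated maxima. That factor assumes a safety sample of 18 and 11 infused, and it moves with the actual numbers. The cause is the missing period split together with the safety-sample denominator. The stray label is a separate drafting error.

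A reader might also want to state what share of tabulated events precedes exposure. The SAP does not support a figure. With infusion at 12 to 14 weeks, the share of observation time before infusion could be as low as 12/104 = 11.5% (counting from the start of withdrawal, two years in the study). It could be as high as 22/74 = 29.7% (the full 8-week screening window, 14 weeks of withdrawal and the minimum 52 weeks of follow-up). The SAP does not say when AE collection starts, and nothing in it supports a constant event rate.

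These are descriptive tables and no test or decision rule depends on them. They should still be corrected, because they carry most of the safety information outside the primary endpoint.

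**What to change.** - **8.2, breakdown.** Replace the treatment-group split with: by period of onset (before IS withdrawal; start of withdrawal to before darTregs infusion; from infusion onward) and overall. State that subjects never infused stay in the second period until they leave the study, and show subject-weeks at risk in each period.
- **8.2, denominator.** Replace the safety-population sentence so that each period uses the subjects entering it: the safety sample before withdrawal and for the overall column, ITT1 for the withdrawal period, and ITT2 from infusion onward. Without this change the old sentence would contradict the new columns.
- **8.2, events spanning infusion.** Flag AEs that begin before infusion and worsen after it. With one record per AE at its highest severity, a split by onset alone would place the worst grade in the pre-infusion period. If the date of worsening is not recorded, flag every AE ongoing at infusion.
- **8.2 and 8.3, SAEs.** Report SAEs related to withdrawal and SAEs related to darTregs on separate lines.
- **8.4.** Replace treatment group with analysis sample.

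The cost is SAP wording and table shells, plus a few more columns with small counts. The 24-week endpoint already requires events to be timed against infusion. The flag for worsening may need a data check or medical review.

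### SAP 8.2 divides darTregs-related and withdrawal-related adverse events by everyone biopsied at screening, not by the subjects exposed (ITT2 and ITT1)

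*SAP*

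**What the plan says.** Section 8.1 sets the default: "All safety analyses will be carried out using the safety sample defined in Section 4 unless otherwise noted". Section 8.2 closes with the rule for its tables: "Percentages will be based on the number of subjects in the safety population". Section 8.3 handles serious events in the same manner.

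Section 4 supplies the samples:
- Safety Sample: "All subjects who give informed consent and undergo the screening liver biopsy (Safety Sample".
- ITT1: "The Intent-to-treat I sample (ITT1) will be defined as all subjects who initiate IS withdrawal".
- ITT2: "The Intent-to-treat II sample (ITT2) will be defined as all subjects who receive darTregs".
- PP: "The Per-Protocol sample (PP) will be defined as all subjects who receive at least" 300 × 10^6 cells.

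The Section 8.2 tables include "Grade 3 or higher Infusion Reactions" among the events of interest, one row that pools SAEs related to withdrawal (ISW) with those related to darTregs, and a table of "AEs by relationship to ISW or darTregs (site investigator determination". No exception to the denominator is stated for any of them.

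The SAP uses ITT2 in 7.2.3, 7.4, 7.5.3 and 7.5.4, but not in 7.3 or in 8.1 to 8.3. The primary safety endpoint, which includes Grade 3 or higher events attributable to the infusion, is analysed on ITT1 (7.3.2) with a PP sensitivity analysis (7.3.3).

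**The concern.** A subject enters the Safety Sample at the screening biopsy, before either intervention. The synopsis expects some to go no further: the biopsy itself can exclude a subject (enrollment exclusion 17), and acute rejection during withdrawal or an unacceptable product bars infusion (infusion exclusions 1 and 4). The accrual row plans for up to 18 enrolled to reach up to 11 eligible for infusion.

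These subjects cannot contribute to the numerator of an infusion-specific row, yet they count in its denominator. Those who never start withdrawal do the same to withdrawal-related rows. The printed percentage is then not the risk among recipients, although the primary safety objective concerns the safety of one darTregs dose. The pooled row has a further problem: its two causes have different populations at risk, so no single denominator suits it.

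**Working it through.** The SAP prints no adverse event percentage, so there is no figure of its own to reproduce. The check asks how far the stated denominator moves a percentage.

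**Inputs.** Up to 18 enrolled and up to 11 eligible for infusion (synopsis, Accrual Objective); nine eligible (synopsis, Study Duration). The numbers actually biopsied and infused are not given, so they are varied as assumptions.

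**Formula.** With x affected subjects, the percentage is x/infused on ITT2 and x/biopsied as written. The relative understatement is 1 − (x/biopsied)/(x/infused) = 1 − infused/biopsied, whatever x is (x > 0).

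| Biopsied | 11 infused | 9 infused |
|---|---|---|
| 12 | 1 − 11/12 = 8.3% | 1 − 9/12 = 25.0% |
| 14 | 1 − 11/14 = 21.4% | 1 − 9/14 = 35.7% |
| 16 | 1 − 11/16 = 31.25% | 1 − 9/16 = 43.75% |
| 18 | 1 − 11/18 = 38.9% | 1 − 9/18 = 50.0% |

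If every biopsied subject is infused, the result is 0%.

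**Absolute size, 11 infused.**
- One affected subject: 1/11 = 9.1% on ITT2, against 1/12 = 8.3% or 1/18 = 5.6%.
- Two affected subjects: 2/11 = 18.2%, against 2/12 = 16.7% or 2/18 = 11.1%.

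Section 8.2 plans no intervals. As an illustration only, the exact (Clopper-Pearson) 95% intervals for one subject are 0.2 to 41.3% (1/11), 0.2 to 38.5% (1/12) and 0.1 to 27.3% (1/18). They overlap widely.

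**Withdrawal-related events.** The same reasoning gives 1 − ITT1/biopsied. The SAP gives no expected size for ITT1. Every infused subject has already started withdrawal, so ITT1 lies between the numbers infused and biopsied, and this understatement lies between 0% and the darTregs figure in the table.

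**The case against.** **Section 7.3 already covers the important events.** In part. PP contains only infused subjects, and 7.3.3 applies it to the endpoint that includes Grade 3 or higher attributable events. If every infused subject receives at least 300 × 10^6 cells, PP equals ITT2. But the SAP provides for smaller doses (6.2 counts them), 7.3.3 does not say whether PP also applies to the individual outcomes, and darTregs-related events below Grade 3 are outside 7.3. The 7.3.2 analysis is on ITT1, which includes subjects never infused.

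**The treatment-group wording in 8.2 gives each column its own N.** It might, if it means analysis sample, as the parallel wording in 8.4 does. But the SAP defines no treatment groups, the closing sentence names one denominator, and the overall summary table has no group columns. The text does not settle it.

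**Readers can recompute.** Largely true: counts stand beside the percentages and 5.1 reports the size of each sample. That limits the harm, but the printed figure is still not the risk among recipients, and the pooled row alone does not separate the two causes.

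**Withdrawal-related rows escape because withdrawal starts before infusion.** A reader might infer this. Timing is not the issue: the Safety Sample also holds subjects who never start withdrawal, so these rows are diluted too, by a different factor.

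**Conclusion.** The concern holds for the percentages of infusion reactions, darTregs-related AEs and SAEs, and withdrawal-related AEs and SAEs in 8.2 and, by reference, 8.3. With 11 infused, the relative understatement for darTregs events runs from 0% (all biopsied subjects infused) through 8% (12 biopsied) and 21% (14) to 39% (18); with 9 infused and 18 biopsied it is 50%. All of this rests on assumed numbers biopsied and infused.

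Two stronger readings are not supported. First, these are relative reductions, not percentage points, and 39% is not a ceiling: it belongs to 11 infused and 18 biopsied, and fewer infused would raise it. Second, a reader might infer that trial safety decisions are compromised. The darTregs adverse event stopping rule uses a count of subjects, event counts do not change, and nothing in the SAP turns on these percentages. The Safety Sample also remains suitable for all-AE tables and for biopsy complications. This is a reporting error that should be corrected before the tables are produced.

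**What to change.** 1. In 8.2 and 8.3, keep the Safety Sample for all-AE tables. Base infusion reactions and darTregs-related AEs and SAEs on ITT2, and withdrawal-related AEs and SAEs on ITT1.
2. Split the pooled SAE row and the relationship table by cause. Count an event judged related to both in each.
3. In 7.3.3, add an ITT2 analysis of the darTregs-attributable component, so that Grade 3 or higher infusion reactions have the same denominator in both sections.
4. In 8.2, replace the treatment-group wording with the named analysis samples, each column using its own N.

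The cost is SAP wording and a few more table rows, with no new data. The percentages become less favourable wherever a biopsied subject was not exposed.
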